## Chapter 10: Data Collection and Monitoring

## 10.1 Case Report Forms and Other Data Collection

1319 The main study data are collected on electronic case report forms (CRFs). When data are directly  
1320 collected in electronic case report forms, this will be considered the source data. For any data  
1321 points for which the eCRF is not considered source (e.g. lab results that are transcribed from a  
1322 printed report into the eCRF), the original source documentation must be maintained in the  
1323 participant's study chart or medical record. This source must be readily verifiable against the  
1324 values entered into eCRF. Even where all study data are directly entered into the eCRFs at office  
1325 visits, evidence of interaction with a live subject must be recorded (e.g., office note, visit record,  
1326 etc.)

1327 Electronic device data files are obtained from the study software and individual hardware  
1328 components. These electronic device files are considered the primary source documentation.

## 10.2 Study Records Retention

1330 Each participating site will maintain appropriate medical and research records for this trial, in  
1331 compliance with ICH E6 and regulatory and institutional requirements for the protection of  
1332 confidentiality of participants.

1333 Study documents should be retained for a minimum of 2 years after the last approval of a  
1334 marketing application in an ICH region and until there are no pending or contemplated marketing  
1335 applications in an ICH region or until at least 2 years have elapsed since the formal  
1336 discontinuation of clinical development of the investigational product. These documents should  
1337 be retained for a longer period, however, if required by local regulations. No records will be  
1338 destroyed without the written consent of the sponsor, if applicable. It is the responsibility of the  
1339 sponsor to inform the investigator when these documents no longer need to be retained.

### 10.3 Quality Assurance and Monitoring

1341 Designated personnel from the Coordinating Center will be responsible for maintaining quality  
1342 assurance (QA) and quality control (QC) systems to ensure that the clinical portion of the trial is  
1343 conducted and data are generated, documented and reported in compliance with the protocol,  
1344 Good Clinical Practice (GCP) and the applicable regulatory requirements, as well as to ensure  
1345 that the rights and wellbeing of trial participants are protected and that the reported trial data are  
1346 accurate, complete, and verifiable. Adverse events will be prioritized for monitoring.

1347 A risk-based monitoring (RBM) plan will be developed and revised as needed during the course  
1348 of the study, consistent with the FDA “Guidance for Industry Oversight of Clinical  
1349 Investigations — A Risk-Based Approach to Monitoring” (August 2013). Study conduct and  
1350 monitoring will conform with 21 Code of Federal Regulations (CFR) 812. This plan describes in  
1351 detail who will conduct the monitoring, at what frequency monitoring will be done, at what level  
1352 of detail monitoring will be performed, and the distribution of monitoring reports.

1353 The data of most importance for monitoring at the site are participant eligibility and adverse  
1354 events. Therefore, the RBM plan will focus on these areas. As much as possible, remote  
1355 monitoring will be performed in real-time with on-site monitoring performed to evaluate the  
1356 verity and completeness of the key site data. Elements of the RBM may include:

- 1357 • Qualification assessment, training, and certification for sites and site personnel
- 1358 • Oversight of Institutional Review Board (IRB) coverage and informed consent procedures
- 1359 • Central (remote) data monitoring: validation of data entry, data edits/audit trail, protocol
- 1360 review of entered data and edits, statistical monitoring, study closeout
- 1361 • On-site monitoring (site visits): source data verification, site visit report
- 1362 • Agent/Device accountability
- 1363 • Communications with site staff
- 1364 • Patient retention and visit completion
- 1365 • Quality control reports
- 1366 • Management of noncompliance
- 1367 • Documenting monitoring activities
- 1368 • Adverse event reporting and monitoring

1369 Coordinating Center representatives or their designees may visit the study facilities at any time in  
1370 order to maintain current and personal knowledge of the study through review of the records,  
1371 comparison with source documents, observation and discussion of the conduct and progress of  
1372 the study. The investigational site will provide direct access to all trial related sites, source  
1373 data/documents, and reports for the purpose of monitoring and auditing by the sponsor, and  
1374 inspection by local and regulatory authorities.

#### 1375 **10.4 Protocol Deviations**

1376 A protocol deviation is any noncompliance with the clinical trial protocol, GCP, or procedure  
1377 requirements. The noncompliance may be either on the part of the participant, the investigator,  
1378 or the study site staff. A significant (or major) deviation is any deviation that departs from the  
1379 established materials in such a way that it poses an increase in the risk to subjects, adversely  
1380 affects the welfare, rights, or safety of the research subjects, or negatively influences the  
1381 scientific study integrity. As a result of a significant deviation, a corrective and preventive action  
1382 plan shall be developed by the site and implemented promptly.

1383 The site PI/study staff is responsible for knowing and adhering to their IRB requirements.  
1384 Further details about the handling of protocol deviations will be included in the monitoring plan.

## 1385                   **Chapter 11: Ethics/Protection of Human Participants**

### 1386                   **11.1 Ethical Standard**

1387                   The investigator will ensure that this study is conducted in full conformity with Regulations for  
1388                   the Protection of Human Participants of Research codified in 45 CFR Part 46, 21 CFR Part 50,  
1389                   21 CFR Part 56, and/or the ICH E6.

### 1390                   **11.2 Institutional Review Boards**

1391                   The protocol, informed consent form(s), recruitment materials, and all participant materials will  
1392                   be submitted to the IRB for review and approval. Approval of both the protocol and the consent  
1393                   form must be obtained before any participant is enrolled. Any amendment to the protocol will  
1394                   require review and approval by the IRB before the changes are implemented to the study. All  
1395                   changes to the consent form will be IRB approved; a determination will be made regarding  
1396                   whether previously consented participants need to be re-consented.

### 1397                   **11.3 Informed Consent Process**

#### 1398                   **11.3.1 Consent Procedures and Documentation**

1399                   Informed consent is a process that is initiated prior to the individual's agreeing to participate in  
1400                   the study and continues throughout the individual's study participation. Extensive discussion of  
1401                   risks and possible benefits of participation will be provided to the participants and their families.  
1402                   Consent forms will be IRB-approved and the participant will be asked to read and review the  
1403                   document. The investigator will explain the research study to the participant and answer any  
1404                   questions that may arise. All participants will receive a verbal explanation in terms suited to  
1405                   their comprehension of the purposes, procedures, and potential risks of the study and of their  
1406                   rights as research participants. Participants will have the opportunity to carefully review the  
1407                   written consent form and ask questions prior to signing.

1408                   The participants should have the opportunity to discuss the study with their surrogates or think  
1409                   about it prior to agreeing to participate. The participant will sign the informed consent document  
1410                   prior to any procedures being done specifically for the study. The participants may withdraw  
1411                   consent at any time throughout the course of the trial. A copy of the informed consent document  
1412                   will be given to the participants for their records. The rights and welfare of the participants will  
1413                   be protected by emphasizing to them that the quality of their medical care will not be adversely  
1414                   affected if they decline to participate in this study.

#### 1415                   **11.3.2 Participant and Data Confidentiality**

1416                   Participant confidentiality is strictly held in trust by the participating investigators, their staff,  
1417                   and the sponsor(s) and their agents. This confidentiality is extended to cover testing of  
1418                   biological samples and genetic tests in addition to the clinical information relating to  
1419                   participants. Therefore, the study protocol, documentation, data, and all other information  
1420                   generated will be held in strict confidence. No information concerning the study or the data will  
1421                   be released to any unauthorized third party without prior written approval of the sponsor.

1422                   The study monitor, other authorized representatives of the sponsor, representatives of the IRB,  
1423                   regulatory agencies or company supplying study product may inspect all documents and records

1424 required to be maintained by the investigator, including but not limited to, medical records  
1425 (office, clinic, or hospital) and pharmacy records for the participants in this study. The clinical  
1426 study site will permit access to such records.

1427 The study participant's contact information will be securely stored at each clinical site for  
1428 internal use during the study. At the end of the study, all records will continue to be kept in a  
1429 secure location for as long a period as dictated by the reviewing IRB, institutional policies, or  
1430 sponsor requirements.

1431 Study participant research data, which is for purposes of statistical analysis and scientific  
1432 reporting, will be transmitted to and stored at the Jaeb Center for Health Research (JCHR). This  
1433 will not include the participant's contact or identifying information, unless otherwise specified in  
1434 the informed consent form. Rather, individual participants and their research data will be  
1435 identified by a unique study identification number. The study data entry and study management  
1436 systems used by clinical sites and by JCHR research staff will be secured and password  
1437 protected. At the end of the study, all study databases will be archived at the JCHR.

1438

## Approvals

Role	Digital Signature or Handwritten Signature/Date
Author and Statistician: [name], JCHR	
Senior Statistician: [name], JCHR	
Coordinating Center Director: [name], JCHR	
Sponsor: [name], Tandem Diabetes Care, Inc.	

29

30           **1. Study Overview**

31  
32       The following table gives an overview of the 2IQ study.  
33

34       **Table 1. Study Overview**

PARTICIPANT AREA	DESCRIPTION
Title	Control-IQ Technology in Individuals with Type 2 Diabetes (2IQ)
Précis	A prospective, single-arm study of 6 weeks of home use of the Control-IQ automated insulin delivery system in individuals with type 2 diabetes age 18 and older.
Investigational Device	t:slim X2 insulin pump with Control-IQ technology v1.5 (Control-IQ System)
Objectives	The objectives of the study are to assess safety and explore glycemic outcomes with use of a closed loop control (CLC) system (t:slim X2 with Control-IQ Technology) in adults with type 2 diabetes to provide data to design a subsequent larger study.
Study Design	After an initial run-in period to ensure that participants can successfully use the study CGM and study pump in open-loop mode, all participants will use the study system (pump and CGM) in closed-loop mode for 6 weeks.
Number of Sites	~3 US clinical centers
Key Safety Endpoints	Key Safety Endpoints: 

• Severe Hypoglycemia

• Diabetic Ketoacidosis and Hyperosmolar Hyperglycemic Syndrome

• Other reportable adverse events

• Unanticipated adverse device effects

Other Endpoints	Other Endpoints: 

• CGM-measured % below 54 mg/dl

• CGM-measured % above 180 mg/dL

• CGM-measured post-prandial glycemic peak

• Various other CGM-measured glycemic outcomes over 24 hours, daytime, and nighttime, as well as CGM outcomes with respect to announced meals

• Total daily insulin use, daily basal and bolus insulin, and Weight

 
Primary and secondary endpoints will be analyzed in total together, as well as separately for Group A (prior users of basal insulin only) and Group B (prior users of multiple daily injections) participants.

Population	Inclusion Criteria 

1. Age <math>\geq</math>18 years old and residing in the US

2. Clinical diagnosis, based on investigator assessment, of type 2 diabetes for at least one year

3. Using a stable insulin dose for at least 3 months, to include A) basal insulin only, or B) MDI, to include CSII (including use of AID systems other than Tandem Control-IQ)

4. Total daily insulin dose <math>\leq</math>200 units/day

PARTICIPANT AREA	DESCRIPTION
	
5. Willing to use only aspart (novolog) or lispro (humalog) insulin with the study pump, with no use of concentrated insulin above U-100, long-acting basal insulin injections, or inhaled insulin
 
6. For females, not currently known to be pregnant If female of child-bearing potential, must agree to use a form of contraception to prevent pregnancy while a participant in the study as documented in the study records. A negative serum or urine pregnancy test will be required for all females of child-bearing potential. Participants who become pregnant will be discontinued from the study. Also, participants who during the study develop and express the intention to become pregnant within the timespan of the study will be discontinued.
 
7. HbA1c <math>\geq 7.5\%</math> and <math>\leq 12\%</math> at screening
 
8. Has current glucagon product to treat severe hypoglycemia (injectable or nasal) at home (will provide prescription if they do not have one)
 
9. Be willing to exercise for 30 minutes or more at least once per week during the main phase of the study
 
10. Has the ability to read and understand written English.
 
11. Investigator believes that the participant has the capacity such that they can provide informed consent and successfully and safely operate all study devices and is capable of adhering to the protocol and completing the study
 
Exclusion Criteria
 
 
1. Prior use of Tandem t:slim X2 insulin pump with Control-IQ technology
 
2. Two or more episodes of severe hypoglycemia (needing assistance) in the past 6 months
 
3. History of inpatient psychiatric treatment in the past 6 months
 
4. History of drug abuse (defined as any illicit drug use) or history of alcohol abuse prior to screening or unwillingness to agree to abstain from illicit drugs throughout the study.
 
5. History of significant heart disease, lung disease, liver disease, chronic kidney disease, or other systemic disease determined by investigator to interfere with the study, or make required exercise unsafe
 
6. History of significant vision, hearing, or dexterity problems that will impair use of the closed loop system
 
7. Use of glucocorticoids, beta blockers, sulfonylureas, meglitinides or other medications specifically listed in section 8.3 of the protocol or determined by investigator to interfere with the study
 
8. Unstable dose of SGLT-2 inhibitor, GLP-1 receptor agonist, or other adjuvant medication specifically listed in section 8.3 of the protocol, or starting a new glucose lowering agent during the trial.
 
9. Unstable dose of any medication used for weight loss, as listed in section 8.3 of the protocol, or starting a new medication for weight loss during the trial.
 
10. Abnormal screening electrocardiogram consistent with increased risk during exercise, such as arrhythmia, ischemia, or prolonged QTc interval (<math>>450</math> ms)
 
11. History of hemodialysis
 
12. History of adrenal insufficiency
 
13. Uncontrolled hypo- or hyperthyroidism
 


PARTICIPANT AREA	DESCRIPTION
	
14. Significant diabetes related complications, based on investigator assessment
 
15. Immediate family member (spouse, biological or legal guardian, child, sibling, parent) who is an investigative site personnel directly affiliated with this study or who is an employee of Tandem Diabetes Care, Inc.

Sample Size	Up to 30 individuals initiating use of the study system in closed-loop mode, with the goal of at least 24 completing the trial
Treatment Groups	All participants will use the study-assigned Control-IQ pump in closed-loop mode.
Participant Duration	~8-12 weeks, depending on duration of run-in phase
Study Duration (planned)	~5 months from first enrollment until last participant visit
Protocol Overview/Synopsis	
After consent is signed, eligibility will be assessed. Eligible participants not currently using a Dexcom G6 CGM or using a Dexcom G6 CGM with <85% of possible glucose values captured during the 14 days prior to enrollment will initiate a CGM run-in phase of 2-4 weeks. Participants who skip or successfully complete the CGM run-in will be trained on use of the study pump in open-loop mode and will initiate a pump run-in phase of 2-4 weeks that will include insulin therapy adjustment to optimize open-loop glycemic control.
 
Participants who successfully complete the open-loop pump run-in will be trained on use of the study pump in closed-loop mode and will use the study system (pump and CGM) in closed-loop mode for 6 weeks.
 
Subjects will be asked to use programmed sleep activity each night and perform exercise challenges with exercise mode enabled at least once per week.
 
Questionnaires will be given at the screening visit after consent; before starting closed-loop use (Control-IQ Phase); and after 6 weeks of closed-loop use. Semi-structured interviews will be performed at the end of the study to better determine the experience of using the study device
 
Study Safety Plan:
 
Participants will be given a blood glucose and ketone meter to use throughout the study, and will be trained on their use by qualified staff. BGM readings will be performed in accordance with the study safety plan and per CGM manufacturer instructions. Ketone readings will be performed per the study safety plan.
 
Site investigators may adjust insulin delivery profile settings as needed throughout the study in accordance with their clinical practice.

39 The following table provides an overview of the schedule of study visits, phone contacts, and key  
40 procedures.

41 **Table 2: Schedule of Visits and Procedures**

42

	Screening Visit	CGM Run-in Visit (may be repeated after 2 weeks)	Pump Training Visit and Settings Optimization (may be repeated after 2 weeks)	Control-IQ Closed-Loop Training Visit	Control-IQ Closed-Loop Use								
					2-4 weeks	2-4 weeks	3d	1w	2w	4w	6w	+3d	UV
Visit (V) or Contact (C)	V	V	V	V	C	C	V	C	V	C	V/C	C	
Informed Consent	X												
Eligibility Assessment	X												
Medical history/physical exam	X												
Height, weight, blood pressure and pulse	X			X 						X 			
HbA1c (POC or local lab)	X												
Central Lab: C-peptide and Glucose; HbA1c	X												
ECG	X												
Pregnancy test (females of child-bearing potential)	X			X									
Questionnaires/Surveys	X		X	X						X			
Semi-structured interview										X 			
Assessment of CGM use	X	X											
Study system training		X	X	X							X		
AE Assessment		X	X	X	X	X	X	X	X	X	X	X	
Upload device data from home					X	X		X				X	
Download device data at clinic visit		X	X	X			X		X			X	

43

44  Interview completed within 28 days of completion of 6-Week visit

45  Weight only

46  Participants will be instructed to contact study staff after each exercise challenge to review AE's and diabetes management around exercise.

47

48

49

## 50 2. Statistical Hypotheses

51

52 The primary outcomes for this study are CGM-measured percentage below 54 mg/dl and CGM-  
53 measured percent above 180 mg/dl over a 6-week period. The intervention will be considered effective  
54 if the 6-week follow-up % above 180 mg/dl value is superior and % below 54 mg/dl value is non-  
55 inferior to the corresponding baseline values using a statistical significance of  $\alpha=0.05$  and the analysis  
56 specified below in Section 7 (i.e.,  $p < 0.05$ ).

57 The null/alternative hypotheses are:

58

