### 79 4.1. Primary Efficacy Endpoint:

80

- 81 Non-inferiority in CGM-measured % below 54 mg/dl between the 6 weeks follow-up. This is the  
82 only non-inferiority and one-sided outcome in the study.
- 83 Superiority in CGM-measured % above 180 mg/dl between the 6 weeks follow-up.

84

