#### 4.3 Calculation of Overall CGM Metrics (primary and secondary):

- One Week of Baseline: The last 7 days of personal CGM data before enrollment or last 7 days of CGM run-in data will serve as baseline. If a participant has <24hr of data in the last 7 days of CGM personal or run-in and if more CGM data are available beyond the 7 days, then will go backwards 24hr at one time until the minimum of 24hr of CGM data are reached. At least 24hr of data during baseline are required for the glycemic metrics to be calculated. These are Dexcom sensor data.
- Six Weeks of CLC use: All CGM data following the midnight of the initiation of CLC use visit day and the midnight right before the end of study visit day will be included irrespective if the system was in closed-loop mode or not. Since the exercise sessions are designed as challenges to the system and the data to be analyzed for safety events, the CGM data between the start of the exercise and 6:00AM next morning will be analyzed separately (see Section 8.1 below) and not included here. On the other hand, since the meals are not designed to be challenges to the system, the CGM data following the meals will be included here even if also analyzed separately (see

Section 8.1 below). If the end of 6 weeks of CLC use visit is more than 6 weeks away from the CLC use initiation visit for a participant, then the CGM data will be truncated at 6 weeks (i.e., 42 days). At least 168hr of data during these 6 weeks of CLC use are required for the glycemic metrics to be calculated and for a participant to be included in the primary and secondary analyses. These are Tandem pump CGM data and will include data following meals and during exercise periods.

- Two-four Weeks of Open Loop (OL) use: All CGM data between the initiation of Open-Loop use and the start of CLC will be used. At least 24hr of data during this period are required for the glycemic metrics to be calculated. These are Tandem pump CGM data.
- All CGM metrics during baseline, OL, and CLC periods will be calculated giving equal weight to each sensor reading for each participant.

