219     • The primary and secondary CGM analyses will include the baseline and the 6-week of CLC use  
220       periods. All p-values that will be calculated refer to these paired baseline-CLC differences.  
221     • All p-values, apart from the primary CGM-measured % below 54 mg/dL, will be two-sided.  
222     • Only CGM metrics, weight/BMI, and some questionnaires are measured both at baseline and  
223       follow-up. As such, p-values will be calculated only for CGM and weight/BMI metrics.  
224     • Standard diagnostics, based on the paired differences between the CLC and baseline periods, will  
225       be performed for all analyses. If the paired differences do not follow an approximate normal  
226       distribution, non-parametric methods will be used.  
227

228 distribution, then a non-parametric comparison based on ranks will be performed. Previous  
229 experience suggests that no nonparametric analyses will be necessary for % time in range 70-180  
230 mg/dL, % above 180 mg/dL, or mean glucose. Other outcomes like % below 54 mg/dL are  
231 skewed; however, the differences between the two periods may follow a normal distribution and  
232 there may be no need for nonparametric analyses.

233 • Exploratory CGM analyses will include all three periods: baseline, OL, and CLC use. No p-  
234 values will be calculated for these exploratory analyses; but only summary statistics like mean  
235 (SD) or median (IQR) and plots.

236

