## 253 **6. Primary Analyses**

254

255 The primary outcomes are non-inferiority in % time below 54 mg/dl and superiority in % time above  
256 180 mg/dl during the 6-week of CLC use when compared with one week of baseline CGM-only use.  
257 Summary statistics (mean  $\pm$  SD or median (quartiles)), scatterplots, and boxplots and will be reported  
258 for the two CGM-measured outcomes at baseline, during 6-weeks of CLC use, and the difference  
259 between the two periods.

260 A paired t-test will be used. Primary analyses will report the point estimate, 95% confidence interval,  
261 and p-value for the paired differences. If the paired differences are highly skewed, then a non-parametric  
262 rank-test, equivalent with a paired t-test, will be used instead. It is expected that the paired differences  
263 for both primary outcomes will follow a normal distribution, even if the % time below 54 mg/dl values  
264 will not.

267 CGM-measured % below 54 mg/dL will be a non-inferiority test with limit +1%. Since non-inferiority is  
268 typically framed in terms of a one-sided test, it is worth noting that the left half of a two-sided test at  
269 alpha = 0.05 gives the same rejection region as a one-sided test at alpha = 0.025. Therefore, reporting a  
270 two-sided 95% confidence interval will provide flexibility to also test for inferiority if non-inferiority  
271 cannot be declared, or superiority if non-inferiority is declared. The following figure shows examples of  
272 the inference to be drawn for a non-inferiority analysis based on the two-sided 95% confidence interval  
273 in various scenarios:  
274

290 **7.2. Insulin Analyses**  
291 Summary statistics appropriate to the distribution for total daily basal, bolus, and insulin and boxplots  
292 will be generated.

293

294 **7.3. Weight and Body Mass Index Analyses**  
295 Summary statistics appropriate to the distribution for weight and BMI will be given at enrollment and  
296 the end of study. A paired t-test or equivalent non-parametric test will be calculated as mentioned above  
297 for the primary outcomes.

298

299 **7.4. Questionnaires**

300 For each questionnaire, summary statistics (mean  $\pm$  SD and n(%)) will be given for each item and at  
301 each time point when the questionnaire was administered. For questionnaires with a scoring guide  
302 available that are administered at both the start of closed loop and again at 6 weeks – that is for DAWN  

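### The success criterion for % below 54 mg/dL reads literally as a one-sided 0.05 test (SAP 2, 4.1, 5.1; Protocol 9.2), but SAP 6 infers from the two-sided 95% CI, i.e. one-sided 0.025

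*SAP*

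**What the plan says.** **Success criterion.** SAP 2 requires superiority on % above 180 mg/dL and, for % below 54 mg/dL, a value that is non-"inferior to the corresponding baseline values using a statistical significance of" 0.05, glossed as p<0.05. One threshold serves both tests and no sidedness is given. Protocol 9.2 carries the same criterion.

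**Sidedness.** SAP 4.1 describes % below 54 mg/dL as the "only non-inferiority and one-sided outcome in the study". SAP 5.1 repeats it for the p-values: "All p-values, apart from the primary CGM-measured % below 54 mg/dL, will be two-sided".

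**Inference.** SAP 6 sets the limit at +1% and says that half of a two-sided test at "alpha = 0.05 gives the same rejection region as a one-sided test at alpha = 0.025". It then introduces a figure showing "the inference to be drawn for a non-inferiority analysis based on the two-sided 95% confidence interval". It also plans to give both kinds of result: "Primary analyses will report the point estimate, 95% confidence interval" and a p-value. No 0.025 threshold is attached to that p-value.

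**Cross-references.** SAP 2 takes its analysis as "specified below in Section 7", but the primary analyses are in SAP 6. Protocol 9.2 points to Section 6, which in the protocol is Testing Procedures and Questionnaires. The protocol's primary analysis is in 9.6, which gives a paired t-test with a rank-based fallback and no CI rule or one-sided level.

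**The concern.** Non-inferiority on % below 54 mg/dL is the hypoglycemia half of a two-part success rule. A one-sided p-value (SAP 4.1, 5.1) compared with 0.05 (SAP 2, Protocol 9.2) is a different test from requiring the upper limit of a two-sided 95% CI to lie below +1% (SAP 6).

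If the one-sided p-value falls from 0.025 up to 0.05, the wording of SAP 2 is met while the CI reported beside it reaches or crosses +1%. Someone working from SAP 2 or from the protocol alone would then claim success, and someone working from SAP 6 would not. A decision threshold should read the same way everywhere before the data are seen.

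**Working it through.** **Inputs from the documents.** Alpha 0.05 and p<0.05 (SAP 2, Protocol 9.2). One-sided p-value (SAP 4.1, 5.1). Two-sided 95% CI, limit +1 percentage point, paired t-test (SAP 6). n = 24 completers to 30 starters (SAP 3). There is no power calculation to reproduce. The documents give no SD for the change in % below 54 mg/dL, so every SD below is an assumption, shown over a range. Differences are taken as normal.

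**1. The plan's own equivalence.** 0.05 / 2 = 0.025. The normal quantile is 1.960 for two-sided 0.05 and also for one-sided 0.025; for one-sided 0.05 it is 1.645. SAP 6 is therefore correct, and its rule is not a one-sided 0.05 test.

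**2. Type I error at the margin.** Simulated with a true difference of exactly +1 point, 400,000 trials:

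| n | one-sided p<0.05 | 95% CI upper limit < +1 |
|---|---|---|
| 24 | 0.0495 | 0.0244 |
| 30 | 0.0497 | 0.0249 |

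About 2.5% of these trials pass the first rule and fail the second. The CI rule agreed with one-sided p<0.025 in every trial.

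**3. Where the rules disagree.** The largest mean rise that passes is 1 − t × SD/√n. For n = 24 (23 df), t = 1.714 at one-sided 0.05 and 2.069 at one-sided 0.025.

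| SD (assumed) | passes at 0.05 up to | passes CI rule up to | band |
|---|---|---|---|
| 0.6 | 0.790 | 0.747 | 0.043 |
| 1.0 | 0.650 | 0.578 | 0.072 |
| 1.5 | 0.475 | 0.367 | 0.109 |

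**4. Probability of passing.** Noncentral t with noncentrality (1 − δ)/(SD/√n), where δ is the true change. Example: SD 1.0, δ = +0.5, n = 24 gives 0.5/(1.0/√24) = 2.449, hence 0.768 versus 0.650.

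| n | SD (assumed) | true change | one-sided 0.05 | one-sided 0.025 |
|---|---|---|---|---|
| 24 | 0.6 | 0 | 100.0% | 100.0% |
| 24 | 1.0 | 0 | 99.9% | 99.7% |
| 24 | 1.5 | 0 | 93.6% | 87.8% |
| 24 | 0.6 | +0.5 | 99.0% | 97.4% |
| 24 | 1.0 | +0.5 | 76.8% | 65.0% |
| 30 | 1.5 | 0 | 97.3% | 94.2% |
| 30 | 1.0 | +0.5 | 84.8% | 75.4% |

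**5. What Protocol 1.1 can and cannot add.** It reports time below range with IQR 0.1–0.6% and 0.2–1.0% in type 2 users of the system. Dividing by 1.349 gives (0.6 − 0.1)/1.349 = 0.37 and (1.0 − 0.2)/1.349 = 0.59. These are spreads of levels, not of changes. The only range named there is 70–180 mg/dL, so they appear to describe time below 70, not below 54. They do not supply the SD needed here.

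**The case against.** The best defence is that SAP 2 does not stand alone: it applies alpha 0.05 through the analysis specified later, and SAP 6 explains how alpha 0.05 works for non-inferiority. On that reading 0.05 is the two-sided level, and SAP 4.1 and 5.1 only describe the direction of the test. The wrong section number in SAP 2 does not hurt this reading. SAP 4.3 says that the exercise data "will be analyzed separately (see Section 8.1 below) and not included here", yet Section 8 is Safety Analyses, so SAP pointers seem to run one section high and SAP 2 most likely means Section 6. Protocol 9.2's Section 6 may likewise be the SAP's number carried over.

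Most of this stands as to intent, and it rules out three stronger readings that a reader might infer:

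- That a one-sided 0.05 test was deliberately planned. No sentence says so; it arises only by joining SAP 2 to SAP 4.1 and 5.1.
- That the plan gives no indication which result decides. SAP 6 names the two-sided 95% CI as the basis of inference. The inference figure and the start of Section 7 were not in the text available for this review and may restate the rule.
- That the mismatch threatens the result. Only the larger assumed SDs, or a true rise near half the margin, make a visible difference, and the documents support neither.

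What the defence does not remove is the wording. SAP 5.1 exempts exactly this p-value from being two-sided, so p<0.05 in SAP 2 cannot simply be read as a two-sided p. A reader of the protocol alone cannot recover the 0.025 level, because Protocol 9.6 has no CI rule. The pilot status and the absence of multiplicity correction do not bear on this: the question is the level of one test, not the number of tests.

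**Conclusion.** The concern holds as a mismatch of wording, and it is minor. The criterion in SAP 2 and Protocol 9.2, combined with SAP 4.1 and 5.1, literally gives one-sided 0.05; SAP 6 gives one-sided 0.025 and is very likely what was meant. The certain consequence is a type I error at the margin of 5% against 2.5%. The likely practical effect is small. At n = 24 with no true change, the two rules differ by 0.2 points in the probability of passing at SD 1.0 and by practically nothing at SD 0.6. The gap reaches about 6 points at SD 1.5 with no change (93.6% − 87.8%), and about 12 points at SD 1.0 with a true +0.5 rise (76.8% − 65.0%). These figures rest on assumed SDs and normal differences. SAP 5.1 itself calls % below 54 mg/dL skewed, although it expects that the differences may be normal.

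**What to change.** In SAP 2, SAP 5.1 and Protocol 9.2, state that non-inferiority on % below 54 mg/dL is declared if the upper limit of the two-sided 95% CI for the paired difference (closed loop minus baseline) is below +1 percentage point, equivalently one-sided p<0.025.

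Add the fallback: if the differences are highly skewed and the rank-based method of SAP 5.1 and 6 is used, the same one-sided 0.025 level applies to the rank test of the paired differences against +1 point, reported with its corresponding 95% CI. Without this sentence, a rule tied only to the CI for the mean would not cover the fallback.

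Correct the cross-reference in SAP 2 from Section 7 to Section 6, and in Protocol 9.2 from Section 6 to Section 9.6.

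The margin, the paired t-test, the sample size and the SAP 6 text stay as they are. The cost is wording only. If SAP 6 is the planned rule, no power is lost; the differences in the probability of passing shown above would be a real loss only if one-sided 0.05 had been intended. In that case SAP 6 would instead need a two-sided 90% CI.
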